13.3 Risks and Benefits of Study Procedures

13.3.1 Verbal Autopsy

As verbal autopsy requires a family member to answer questions about a deceased loved one, he or she might experience emotional stress and grief related to the death of the child. Interviewers will be trained to address these situations appropriately with awareness of the cultural context before they are allowed to conduct these verbal autopsies. If the family member is in need of a mental health intervention, referrals will be made by the interviewer.

13.3.2 Swabbing Procedures

There are minimal risks to the participant who receives nasopharyngeal, and nares swabbing. Participants may experience some temporary discomfort, but the swabbing involves minimal risk. Any adverse effects, such as nose-bleeds, will be treated immediately by the examiners. Other health care will be provided at no cost to the study participant if necessary to address a study-related adverse health event.

13.3.3 Stool Collection

Stool samples have been collected in this setting before, with essentially no risk to participants.

13.3.4 Blood Testing

Blood testing will include a pin prick to the finger or heel. The major risk of this procedure is infection at the puncture site, though using aseptic technique will minimize this occurrence. Individuals in these communities are familiar with this procedure because all children who present at a health center with fever are offered the pinprick for a malaria thick smear.

13.3.5 Anthropometric Measurements

There are minimal risks associated with the measuring board, scale, or MUAC tapes aside from anxiety during the measurements. Examiners will do their best to ensure that the parent/guardian of the child understands the process of assessing anthropometric measurements. The examiners will attempt to minimize discomfort for all study participants before, during, and after the measurements are taken. Children with wasting, stunting, malaria, or anemia will be referred for appropriate treatment at the nearest health center.

13 Chapter 14: Study Monitoring

The project will be continuously monitored by the supervisory team, which will consist of members from CRSN and UCSF. The supervisory team will conduct regular monitoring visits to study site locations, with UCSF team members accompanying CRSN team members at least biannually.

14 Chapter 15: Data and Safety Monitoring Committee Charter

This Charter is for the Data Safety and Monitoring Committee (DSMC) for *Mortality Reduction after Oral Azithromycin II Burkina Faso* (MORDOR II Burkina): OPP1187628.

The Charter will define the primary responsibilities of the DSMC, its relationship with other trial components, its membership, and the purpose and timing of its meetings. The Charter will also provide the procedures for ensuring confidentiality and communication, statistical monitoring guidelines to be implemented by the DSMC, and an outline of the content of the Open and Closed Reports that will be provided to the DSMC.

15.1 Primary Responsibilities of the DSMC

The DSMC will be responsible for safeguarding the interests of trial participants, assessing the safety and efficacy of the interventions during the trial, and monitoring the overall conduct of the trial. The DSMC will provide recommendations about stopping or continuing the trial. To contribute to the integrity of the trial, the DSMC may also formulate recommendations relating to the selection/recruitment/retention of participants, to protocol-specified regimens, and the procedures for data management and quality control.

The DSMC will be advisory to the trial leadership group, hereafter referred to as the Steering Committee (SC). The SC will be responsible for promptly reviewing the DSMC recommendations and determining, whether to continue or terminate the trial, and to determine whether amendments to the protocol are required. If needed, the DSMC may seek the advice of a content expert outside of the committee.

15.2 DSMC Membership

The DSMC is an independent multidisciplinary group consisting of epidemiologists, biostatisticians, bioethicists, and clinicians that collectively has experience in the management of infectious diseases and in the conduct and monitoring of randomized clinical trials including subsaharan Africa.

15.3 Conflicts of Interest

The DSMC membership has been restricted to individuals free of apparent conflicts of interest. The source of these conflicts may be financial, scientific, or regulatory. Thus, neither study investigators nor individuals employed by the sponsor, nor individuals who might have regulatory responsibilities for the trial products, are members of the DSMC.

The DSMC members will disclose to fellow members any consulting agreements or financial interests they have with the sponsor of the trial, with the contract research organizations (CRO) , or with other sponsors having products that are being evaluated or that are competitive with those in the trial. The DSMC will be responsible for deciding whether these consulting agreements or financial interests materially impact their objectivity.

The DSMC members will be responsible for advising fellow members of any changes in any of the membership requirements that occur during the course of the trial. It may be appropriate for DSMC members who develop significant conflicts of interest resign from the DSMC.

DSMC membership is to be for the full duration of the trial. If any members leave the DSMC, the SC, in consultation with the DSMC, will promptly appoint a replacement.

15.4 Timing and Purpose of the DSMC Meetings

Organizational Meeting

The initial meeting of the DSMC will be an Organizational Meeting. This is during the final stages of protocol development and the purpose is to provide advisory review of scientific and ethical issues relating to study design to discuss the standard operating procedures and to discuss the format and content of the Open and Closed Reports that will be used to present trial results.

The Organizational Meeting will be attended by all DSMC members, lead trial investigators, and the trial biostatistician. The DSMC will be given the drafts of the trial protocol, the Statistical Analysis Plan, the DSMC Charter, and the

current version of the case report forms. At subsequent meetings, committee members will receive Open and Closed Data Reports.

Formal Interim Analysis Meetings

One or more 'Formal Interim Analysis' meetings will be held to review data relating to treatment safety and efficacy, and quality of trial conduct. There will be at least two interim decisions to be made by the DSMC, at approximately 12 months and 24 months into the study.

15.5 Procedures to Ensure Confidentiality and Proper Communication

To enhance the integrity and credibility of the trial, procedures will be implemented to ensure the DSMC has access to all emerging information from the trial regarding comparative results of efficacy and safety, aggregated by treatment arm.

Closed Sessions

Sessions involving only DSMC members and, where appropriate, those unmasked trial investigators (on the Data Coordinating Committee) who generate the Closed Reports (called Closed Sessions) will be held to allow discussion of confidential data from the trial, including information about the relative efficacy and safety of interventions.

At a final Closed Session, the DSMC will develop a consensus on its list of recommendations, including that relating to whether the trial should continue.

Open Session

In order for the DSMC to have access to information provided, by study investigators, or members of regulatory authorities, a joint session between these individuals and DSMC members will be held between the Closed Sessions.

Open and Closed Reports

For each DSMC meeting, Open and Closed Reports will be provided. Open Reports, will include data on recruitment and baseline characteristics, pooled data on eligibility violations, and completeness of follow-up and compliance. The study statistician (TCP) will prepare these Open Reports.

Closed reports, available only to those attending the Closed Sessions of the meeting, will include analyses of primary and secondary efficacy endpoints, including subgroup and adjusted analyses, AEs and symptom severity, , and Open Report analyses that are displayed by intervention group. These Closed Reports will be prepared by the study biostatistician.

The Open and Closed Reports should provide information that is accurate, with follow-up that is complete to within two months of the date of the DSMC meeting. The Reports should be provided to DSMC members approximately three days prior to the date of the meeting.

Minutes of the DSMC Meeting

The research team will prepare minutes for the open portion of the meeting, including the DSMC's recommendations.

Recommendations to the Steering Committee (SC)

At each meeting of the DSMC during the trial, the committee will make a recommendation to the Steering Committee to continue or terminate. This recommendation will be based primarily on safety and efficacy considerations and will be guided by statistical monitoring guidelines defined in this Charter.

Recommendations to amend the protocol or conduct of the study made by the DSMC will be considered and accepted or rejected by the SC. The SC will be responsible for deciding whether to continue or to stop the trial based on the DSMC recommendations.

The DSMC will be notified of all changes to the protocol or to study conduct. The DSMC concurrence will be sought on all substantive recommendations or changes to the protocol or study conduct prior to implementation.

The SC may communicate information in the Open Report to the sponsor and may inform them of the DSMC recommended alterations to study conduct or early trial termination in instances in which the SC has reached a final decision agreeing with the recommendation. The SC will maintain confidentiality of all information it receives other than that contained in the Open Reports until after the trial is completed or until a decision for early termination has been made.

15.6 Statistical Monitoring Guidelines

The SC will propose statistical rules for a futility stopping rule (requested by the sponsor) and an efficacy stopping rule at the first DSMC meeting. A decision will be made whether the efficacy stopping rule is appropriate for the relatively short, 2-year study.

16.1 Scope of Data

Mortality and morbidity data will be collected in this trial. Mortality data includes: census, mortality, and treatment. Morbidity and resistance data includes the following: census, mortality, treatment, and morbidity assessments.

Mortality Data

Trained census workers will collect census data on all households in the study sites (name, birthdate, age, gender of all household members) and keep track of births, deaths, and migration of children eligible for treatment. In addition to biannual census updates, trained community health workers and study supervisors will conduct WHO verbal autopsy interviews through the duration of the study to provide information on the cause of death. Trained distribution teams will collect data on treatment status and dose given to all study participants, if treatment is provided apart from the time of census.

Mortality-Plus Data

Trained health workers will collect data on core morbidity assessments such as blood samples (thick smears and dried blood spots for malaria, microcuvettes for hemoglobin), stool samples, and nasopharyngeal swabs. Note that for de-identification purposes a random number sticker will be affixed to each specimen collected. In addition, before sample collection, parents or guardians will be asked a standardized series of questions to determine whether the child has had recent fever, cough, or diarrhea. Clinic-based case finding will be conducted at local health clinics, which will involve transcription of health records.

Certain morbidity assessments will be entered into handheld mobile devices at the time of the examination (e.g. hemoglobin, responses to symptom questionnaire), while lab results for thick smears, dried blood spots, nasal, nasopharyngeal, and stool specimens will be entered after confirmation.

16.2 Data Storage, Management, and Security

Data will be recorded electronically using handheld mobile devices with custom-made software applications and uploaded daily onto a secure, password protected, central server. Rapid transfer of electronically captured data will allow nearly real-time monitoring of activity at the study site. All handheld devices and data entry coordinating centers will be password protected, and all changes in data will be noted, including the date of the change, and the person who made the change. To ensure the quality of the data, we will conduct training sessions before each biannual census where needed. The central database application will

MORDOR II Study

Manual of Operations and Procedures

use hard disk encryption and physical protection of the server (which is to be maintained in a locked room accessible only to authorized personnel). The database will be based on mySQL (which supports standard SQL queries). Data will be backed up off site (providing integrity in case of the physical loss of the server). Data will never be deleted from mobile capture devices until at least one offsite backup has been completed. Data security during electronic transfer will be achieved through use of the Advanced Encryption Standard (AES).

16.3 Data Monitoring and Cleaning

Data monitoring and cleaning will be overseen by the data coordinating center (DCC) at the coordinating site. Data collection will be monitored on a weekly basis by the site study coordinator using the dashboard function on Survey solutions. The survey solution dashboard will consist of the following reports by study site: Date Household Census Completed, Number of Households Census Completed by Village, Percent Household Census Completed by village, Treatment Status by Worker, Age Distribution by Worker, Sex Distribution by Worker, GPS Missing by Worker, GPS Missing by Village, Number of Records Synced by Date, Assigned Treatment by Given Treatment, Treatment Status by Age, Treatment Status by Village, Age Distribution by Village, and Sex Distribution by Village.

The DCC will ensure that the site study coordinators log on to Survey solution weekly to confirm the status of the dashboard. In addition, upon each village census completion, the DCC will create and maintain a Stata program to identify data quality concerns. Any such concerns which must be addressed at the site specific level will be queried by the DCC. At every phase, as each village is completed and the data is considered cleaned, the data will be locked and a list of deaths will be generated and provided to each site for verbal autopsy.

16 Appendix

Appendix 1. SAP

Appendix 2. Infant Adverse Events survey

Appendix 3. Pfizer Investigator Initiated Research Serious Adverse Event Report Form and Completion Guide

CHAT:

[figure not shown]
A community-randomized trial

February 13, 2023

Version 1.6

Statistical Analysis Plan

UCSF Francis I. Proctor Foundation
Centre de Recherche en Sante de Nouna
University of Heidelberg

Introduction

This document (Statistical Analysis Plan, SAP) describes the planned analysis and reporting for the clinical trial, **Azithromycin for the prevention of post-neonatal childhood mortality in Burkina Faso: a community-randomized trial**. It includes specifications for the statistical analyses and tables to be prepared for the interim and final Clinical Study Report. This study is designed to compare methods to reduce childhood mortality using mass administration of azithromycin (Pfizer, CAS 83905-01-5) compared to placebo. The content of this Statistical Analysis Plan meets the requirements stated by the US Food and Drug Administration and conforms to the American Statistical Association's Ethical Guidelines.

The following documents were reviewed in preparation of this Statistical Analysis Plan:

- Azithromycin for the prevention of infant and child mortality in Burkina Faso: a community-randomized trial, Manual of Operations
- Azithromycin for the Prevention of Neonatal, Infant, and Child Mortality in Burkina Faso and Safety Assessment, Proposal
- Statistical Analysis Plan, MORDOR Trial
- ICH Guidance on Statistical Principles for Clinical Trials

The planned analyses described in this SAP will be included in future manuscripts. Exploratory analyses not necessarily identified in this Statistical Analysis Plan may be performed to support the analysis. Unplanned analyses not delineated in this Statistical Analysis Plan will be documented as such in the final Clinical Study Report and manuscripts.

This document will be reviewed prior to the enrollment of patients. All subsequent changes will be indicated by detailed change log in the Appendix.

Contents

1	Summary	4
1.1	Mortality Trial	4
2	Statistical Analysis	4
2.1	Planned Analyses	4
2.1.1	Mortality Trial	4
2.2	Interim Monitoring	7
3	Sample Size Considerations	8
4	Randomization	10
5	Abbreviations	11
6	Revision History	12

1 Summary

1.1 Mortality Trial

The trial profile is given in the Manual of Operations. In the mortality trial, communities are randomized to two arms: **Azithro** and **Placebo**. The trial is a placebo-controlled, double-masked (i.e., double-blind), community-randomized, clinical trial.

Objective. Determine the efficacy of biannual mass azithromycin distribution versus placebo in children aged 1–59 months on all-cause mortality. *We hypothesize that biannual distribution of azithromycin will lead to significantly reduced all-cause mortality among children aged 1–59 months after 36 months of treatment.*

2 Statistical Analysis

2.1 Planned Analyses

2.1.1 Mortality Trial

The primary prespecified analysis will use the number of deaths in each community as the outcome variable. For analysis, a death is counted when an individual in the target age range 1–59 months is enumerated as alive on census i ($i = 0, 1, 2, 3$) and is not on census $i + 1$ due to death. Census i takes place at the beginning of the study, and each subsequent census takes place approximately six months later.

Primary Analysis.

The primary analysis will be conducted as **negative binomial regression**. The number of person-years (for persons in the target age range) is derived by summing the person-times for each period. The community-level predictor consists of treatment arm for the community. Specifically, the treatment variable is a community level variable, not an individual level variable. The statistical significance assessed by permutation testing at the level of the randomization unit.

Individuals who are in the target age range at the beginning of any study period, but who are no longer in the target age range by the end, are considered to be fully enrolled and contribute the full amount of person-time for that period.

The analysis will be **two-sided**, with a **type I error rate** (alpha) of 0.05.

Statistical considerations.

- Statistical tests will be conducted with Monte Carlo permutation based on the randomization unit. The number of replications will be 10,000, unless the Monte Carlo confidence interval for the P-value includes 0.05. In this case, 10,000,000 will be used, and this fact reported.
- Tests for interaction by age sub-groups and by phase on the additive scale will be conducted to evaluate for statistically significant subgroup differences.
- Model adequacy will be checked by examination of residuals or other goodness of fit tests as needed. Inadequate model fit will prompt us to report alternative models.
- For negative binomial regression, an aggregation parameter of 30 or greater will cause us to re-fit using Poisson regression.
- Multiple imputation will be used in case of missing baseline covariates (if applicable). Missing outcome variables will be handled by sensitivity analysis and reporting of conditional results.
- Individual level missing data (due to loss to follow-up or dropouts) is expected. If an individual is lost to follow-up or otherwise unavailable during an interval of length D , then the individual will not be assigned any amount of person time. If an individual dies within an interval of length D , then the individual is assumed to contribute the amount of person-time $D/2$ to the denominator (midpoint imputation).
- Village-level missing data could occur for various reasons, including field error, withdrawal of support from village leadership, or other unforeseen reasons. The analytic

plan will be to analyze all available information (including data from any community prior to the time of dropout of that community). If a community drops out and then re-enters, all available data (before and after the dropout period) will be analyzed.

Supplementary analyses.

The purpose of the supplementary analyses reported in this section is to assess the role of statistical choices and data quality choices in shaping the result.

survival Cox proportional hazard regression of time to death, with inference based on permutation test of randomization unit

Secondary analyses of mortality.

All secondary analyses will be sharply distinguished from the primary prespecified analysis and will be identified as such. Secondary analyses include outcome variables or planned subsets which contribute either additional insight or address different scientific questions than the primary analysis.

age Poisson regression at the individual level, clustering on community, including age as a covariate (we will both adjust for age, as well as examine age-treatment interactions)

age Negative binomial regression, reporting using the same age categories as in MORDOR Niger/Malawi/Tanzania (1–5 months, 6–11 months, 12–23 months, 24–59 months)

timing Cramer–von Mises comparison of death time conditional on mortality, between arms; comparison of death time density between arms

the number of azithromycin doses received Logistic regression at the individual level, clustering on community, using the number of azithromycin doses as the primary predictor

factorial analysis Logistic regression at the individual level, clustering on community, using the interaction term for the two factors, the community and individual arms

Additional secondary outcomes.

nutritional status Weight, height, and MUAC will be analyzed. MUAC will be compared between arms using clustered linear regression (clustered on community). MUAC will be available in all 341 communities; weight and height will only be available in specific prespecified communities which are located in the HDSS.

malaria Malaria parasitemia is assessed using thick smears. The available data will be the fraction of the sampled children who are positive. This is a longitudinally measured fraction, and we propose modeling this using clustered linear regression on square-root transformed data (with clustered logistic regression as a sensitivity analysis). These data are only available in the 48 HDSS communities.

antibiotic resistance Like malaria parasitemia, phenotypic antibiotic resistance is a binary outcome at the individual level, and a fraction at the community level. The same analytic template as for malaria parasitemia will be used.

microbiome Intestinal and nasopharyngeal microbiome will be assessed. We propose to examine L2-norm (Euclidean) distance using PERMANOVA with permutations at the level of the randomization unit. We will also also examine L1 and diversities (L2 and L1, or Simpson's and Shannon's). This outcome, like malaria and antibiotic resistance, is only available in the 48 communities in the HDSS.

cause of death A verbal autopsy questionnaire for children will be used to collect data for verbal autopsies[?]; details are provided in the MOP. Cause of death will be assigned according to an algorithm based on a published verbal autopsy hierarchy. Cause of death will be compared with the use of the chi-square statistic, with clustering taken into account by community-level, using a permutation test to obtain the p-value.

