1.2. Objectives

- 1: Determine the efficacy of biannual mass azithromycin distribution versus placebo in children aged 1-59 months for reduction in all-cause mortality. *We hypothesize that biannual distribution of azithromycin will lead to significantly reduced all-cause mortality among children aged 1-59 months after 36 months of treatment.*
- 2: Determine the efficacy of targeted azithromycin distribution to infants during an early infant healthcare visit (approximately 5th through 12th week of life) on infant mortality. *We hypothesize that infants receiving a single dose of azithromycin during early post-neonatal infancy will have significantly lower all-cause mortality compared to infants receiving placebo.*
- 3: Determine the mechanism behind the effect of biannual mass azithromycin distribution for reduction in child mortality.

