2.2 Interim Monitoring

Efficacy. The trial is designed specifically to collect three years of data, because of

interest in whether the treatment effect is durable after the first. However, in case of a large effect found after one year, it may be desirable to expand treatment to all communities.

A single interim analysis conducted at alpha of 0.001 will be conducted. Specifically, the interim analysis will be conducted when mortality data are available for the first year (two study periods).

The final analysis would be conducted at alpha 0.049.

Futility. An interim analysis of futility is proposed, to be finalized in consultation with the Data and Safety Monitoring Board. Specifically, we propose to conduct negative binomial regression on village-level mortality counts comparing the treatment and control arms (using a common aggregation parameter) using only data from the first year. This analysis will be conducted using simulation. We suggest consideration of the conditional power to detect a 30% effect. If this drops below 20% at the interim analysis, discontinuation of the trial or other changes to the protocol may be made in consultation with the Data and Safety Monitoring Board.

Interim analysis will be executed by the trial biostatistician at the central site.

3 Sample Size Considerations

We use the following formula (cited from [?]):

$$c = 1 + (z_{\alpha/2} + z_{\beta})^2 \frac{(\lambda_0 + \lambda_1)/y + k^2(\lambda_0^2 + \lambda_1^2)}{(\lambda_0 - \lambda_1)^2}$$

where

c is the number of clusters per arm,

y is the number of person-years per cluster,

λ_0 is the rate in the control group,

λ_1 is the rate in the treatment group,

k is the coefficient of variation in both groups,

α is the alpha level,

β and is the type II error rate.

- The base rate for mortality is assumed to be 0.02 per year in the target age range.
- We assume the same coefficient of variation for village-level mortality as for the Niger site, i.e. 0.34.
- We assume that 16.7% of the population is in the target range of 1–59 months.
- We assume an average community size of 1000 people.
- We assume 10% loss to follow-up per year.
- The effect size is 0.1365.

The number of clusters per arm for Burkina Faso is 170, and the total number of clusters for Burkina Faso is 340.

The sample size is fixed at 341 clusters at the begining of the study.

We estimate that 341 clusters will provide 80% power to detect a 13.65% reduction in mortality in 1-59 month age group.

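### The primary-outcome definition stops counting deaths at month 24, while the hypothesis and design run to month 36

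*SAP*

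**What the plan says.** SAP 2.1.1 defines the primary outcome. A death counts when a child aged 1–59 months "is enumerated as alive on census i ($i = 0, 1, 2, 3") and is absent from census i + 1 because of death. The next sentence reads "Census i takes place at the beginning of the study" and spaces later censuses about six months apart. SAP 2.2 confirms the spacing by timing the interim analysis for when "mortality data are available for the first year (two study periods").

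The other statements of horizon in the SAP say three years. The objective in SAP 1.1 is reduced "all-cause mortality among children aged 1–59 months after 36 months of treatment", and SAP 2.2 says "The trial is designed specifically to collect three years of data". SAP section 3 states "The number of clusters per arm for Burkina Faso is 170" but gives neither the person-years per cluster nor the horizon behind that figure.

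The protocol mostly agrees with three years. Section 1.2 repeats the hypothesis ("all-cause mortality among children aged 1-59 months after 36 months of treatment"), Chapter 3 describes mortality assessment over three years, and Table 1 in section 4.2 lists censuses at months 0, 6, 12, 18, 24, 30 and 36. Section 6.2 likewise counts seven study visits. Two places differ: Eligible Individuals, in Chapter 4, describes seven segments of six months, and section 15.6 of the monitoring committee charter calls the trial a two-year study.

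**The concern.** This sentence decides which deaths enter the primary test, and it conflicts with the hypothesis that test is meant to address. An analyst who follows the index leaves out the last year of deaths. One who follows the hypothesis departs from the written definition of a death.

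The protocol does not settle the matter cleanly, because a reader can find 24, 36 and 42 months in the two documents. If the horizon is chosen only once results are known, the choice can be called data-driven.

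**Working it through.** **Horizon.** The largest index is 3, so the last interval ends at census 3 + 1 = 4, and 4 × 6 = month 24. Month 36 is census 36/6 = 6, which needs i = 0 to 5. The omitted intervals are months 24–30 and 30–36. The month-36 visit gives azithromycin to all children without placebo (protocol 5.1.1), so no placebo-controlled interval follows it. That supports six intervals rather than seven. No entry in the SAP revision history touches the index.

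**Inputs (SAP section 3).** λ0 = 0.02; effect 0.1365, so λ1 = 0.02 × 0.8635 = 0.01727; k = 0.34; two-sided α = 0.05; power 0.80; 1000 people × 0.167 = 167 children per cluster; 10% loss per year.

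**The SAP's formula.** c = 1 + (z_α/2 + z_β)² [(λ0 + λ1)/y + k²(λ0² + λ1²)] / (λ0 − λ1)²

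- (z_α/2 + z_β)² = (1.960 + 0.842)² = 7.849
- λ0 + λ1 = 0.03727
- k²(λ0² + λ1²) = 0.1156 × 0.00069825 = 0.00008072
- (λ0 − λ1)² = 0.00273² = 0.0000074529

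This reduces to c = 86.01 + 39,250/y.

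**Reproducing 170 per arm.** Setting c = 170 gives y = 39,250/83.99 = 467 person-years per cluster. Three years with a flat 10% reduction gives y = 167 × 3 × 0.9 = 450.9 and c = 173.1, within 2% of the stated figure. Two years with no loss at all gives y = 334 and c = 203.5, so 24 months cannot produce 170.

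**Range.** The SAP does not say how the 10% loss enters y, so I applied it in ten ways: no loss; flat 0.9; yearly retention of 1, 0.9, 0.81; yearly retention of 0.9, 0.81, 0.729; the average of each year's start and end; half-yearly steps taken at the start or at the end of each half-year; continuous decay; T × 0.9^T; and T × (1 − 0.1T).

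| Horizon | Clusters needed per arm |
|---|---|
| 24 months | 204–233 |
| 36 months | 164–198 |
| 42 months | 153–189 |

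Some 42-month variants land close to 170 (168.5 and 170.9). The sizing therefore rules out 24 months but does not by itself identify 36.

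**Power if deaths and person-time both stop at month 24.** Power = Φ(√{(c − 1)(λ0 − λ1)² / [(λ0 + λ1)/y + k²(λ0² + λ1²)]} − 1.960), with c = 341/2 = 170.5.

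- 36 months, flat 10% loss, y = 450.9: √(0.0012633/0.00016338) = 2.781, power 0.794.
- 24 months, flat 10% loss, y = 300.6: √(0.0012633/0.00020470) = 2.484, power 0.700.
- All ten variants: 0.74–0.81 falls to 0.67–0.73, a loss of 7.0 to 9.4 points.

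The share of person-time after month 24 is 24–33%, and at a constant rate so is the share of expected deaths. Under flat loss and a mean rate of 0.018635, expected deaths are 341 × 450.9 × 0.018635 ≈ 2,865 to month 36 and 341 × 300.6 × 0.018635 ≈ 1,910 to month 24.

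Protocol Chapter 3 gives 278 communities rather than 341. With c = 139 and the same cluster size, flat-loss power falls from 0.709 to 0.611, and the loss over the ten variants is 7.0 to 9.8 points.

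**The case against.** The best defence is that this is a clerical slip with little practical risk. The SAP states the 36-month horizon twice, the protocol states it several times, and a statistician holding six intervals of data is unlikely to discard two because of one parenthesis. The adjacent error about census i points to weak proofreading rather than a rival estimand. This is fair as to likelihood, and it is why the power loss is a worst case. It does not make the written definition right. The SAP's rule to analyze all available information does not help either, because it covers villages that drop out and does not redefine a countable death.

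A second point is that the index sits only in the death-counting sentence, and person-time is summed over periods with no stated limit. That stands: cutting person-time at month 24 is an inference. It is the natural reading, since the person-time rule works on the same inter-census intervals ("If an individual dies within an interval of length D"), and the power figures depend on it.

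A third is that children enter afresh at each census, so loss need not accumulate, and the harsher loss variants overstate it. That is also reasonable, and the flat 10% case is probably nearest the design. It gives the largest drop at 341 clusters, 9.4 points.

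Finally, 278 versus 341 is a separate discrepancy, and a community count need not equal a count of randomization units. The 278 figures show only that the size of the loss does not depend much on which number is used.

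**Conclusion.** The definition is wrong as written. It ends the primary death count at month 24, against the SAP's own 36-month hypothesis and three-year design, and nothing elsewhere in either document corrects it. The case for i = 0 to 5 rests on the stated hypothesis, the three-year statement and the seven-census schedule. The sample size adds that two years is not possible.

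The contradiction needs no assumption beyond the six-month spacing. The consequence for power does: it requires that deaths and person-time are both truncated, and it varies with how loss enters y. Because this sentence defines the primary outcome, it must be corrected even though the literal reading may never be applied.

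**What to change.** In SAP 2.1.1, set i = 0, 1, 2, 3, 4, 5 and state that deaths and person-time both cover the six intervals from census 0 to census 6, months 0 to 36. In the next sentence, name census 0 as the one at the start of the study. In SAP section 3, state y and the horizon used.

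Log the change in the revision history. Version 1.6 is dated February 2023, after the month-36 round scheduled for February to July 2022, so the entry should also say whether anyone deciding the change had seen results by arm.

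In the protocol, reconcile the seven segments in Eligible Individuals and the two-year description in section 15.6 with the same horizon.

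The cost is two corrected SAP sentences, one added line, one revision entry and two protocol edits. No new data are needed.
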